## 8. SAFETY ANALYSES

The safety analyses will be based on the Safety population, unless otherwise specified.

### 8.1. Secondary Safety Analyses

#### *Blood Pressure*

Secondary Safety Statistical Analyses: Blood Pressure
Endpoint(s)

 
• Change from baseline in SBP, DBP and MAP at Week 52 and at the end of study treatment
 
• Number of BP exacerbation events per 100 patient years
 
• N (%) of subjects with at least one BP exacerbation event during study
 
 
NOTE: Unless otherwise specified, for summaries and analyses of BP values, the post-dialysis BP values for subjects will be used.

Model Specification

 
• The difference in change from baseline in BP (SBP, DBP, and MAP) at Week 52 will be analyzed with a mixed model repeated measures (MMRM) approach with an unstructured covariance matrix to compare the difference in means between arms. The models will be fitted to scheduled BP data collected after baseline up to Week 52 (including Week 52 visit). Models will be run four times: 
 
○ On-treatment BP values only, excluding values collected during the stabilization period (post-baseline up to but excluding Week 28 visit).
 
○ On-treatment BP values only, including values collected during the stabilization period.
 
○ On- and off-treatment BP values, excluding values collected during the stabilization period.
 
○ On- and off-treatment BP values, including values collected during the stabilization period.
 
 
 
• The models will include factors for treatment, time, prognostic randomization stratification factor (Region, see Section 5.3), baseline BP parameter and the baseline BP parameter by time and treatment by time interaction terms. Analyses will be done with the MIXED procedure in SAS, using the Kenward-Roger option to estimate denominator degrees of freedom and standard errors. For analyses using on- and off-treatment values, subjects who withdraw from the study before Week 52 are considered to be missing at random and in the analysis using on-treatment values only, subjects who permanently discontinue study treatment before Week 52 are assumed to be missing at random.
 
• The difference in change from baseline in BP (SBP, DBP, and MAP) at the derived end of treatment (see Section 14.6.4) will be analyzed with an ANCOVA model including terms for treatment, prognostic randomization stratification factor (Region, see Section 5.3) and the corresponding baseline BP parameter. This analysis will be performed using on-treatment BP values only.
 
• The number of on-treatment BP exacerbation events per 100 patient years will be calculated (see Section 14.6.4). Confidence intervals for the rate per 100 patient years will also be reported. For within group rates and the ratio of model estimated exacerbation rates, the point estimates, two-sided 95% confidence intervals, and one-sided p-value for the treatment group
 

CONFIDENTIAL

204837

Secondary Safety Statistical Analyses: Blood Pressure
comparison will be obtained using a negative binomial model with treatment and the prognostic randomization strata as covariates and the logarithm of time on-treatment as an offset variable.
Model Results Presentation

 
• BP parameter values (SBP, DBP, and MAP) will be summarized using mean, standard deviation, minimum, P25, median, P75, and maximum at each visit by treatment group. In addition to scheduled visits, the derived baseline value, and end of treatment values will be summarized (see Section 14.6.4). Summaries of on-treatment BP values only and on- and off-treatment BP values together will be produced for both pre- and post-dialysis BP. On-treatment BP parameter values will be plotted by visit using a line plot.
 
• BP parameter change from baseline values (SBP, DBP, and MAP) will be summarized using mean, standard deviation, minimum, P25, median, P75, and maximum at each post-baseline visit by treatment group. In addition to scheduled visits, the derived end of treatment values will be summarized (see Section 14.6.4). Summaries of on-treatment BP values only and on- and off-treatment BP values together will be produced for both pre- and post-dialysis BP. On-treatment BP parameter change from baseline values will be plotted by visit using a line plot.
 
• For the MMRM analyses of change from baseline in BP parameters to Week 52, an LSMEANS statement will provide adjusted treatment group means, standard errors, a point estimate, a two-sided 95% confidence interval for the adjusted mean treatment difference (daprodustat - rhEPO), and a one-sided superiority p-value for this test.
 
• For the ANCOVA analyses of change from baseline in BP parameters to the derived end of treatment, the adjusted mean estimates and standard errors by treatment group, adjusted mean difference, two-sided 95% CI and one-sided superiority p-value for the difference in BP parameter between the daprodustat and rhEPO arms from the ANCOVA model will be presented. The number of subjects contributing to the analysis and the associated mean and standard deviation of the baseline and end of treatment values will also be displayed with the results of the ANCOVA model.
 
• The model estimated on-treatment BP exacerbation rates per 100 patient years and associated 95% confidence intervals will be provided by treatment group. The ratio of model estimated on-treatment BP exacerbation rates and associated two-sided 95% confidence interval and one-sided p-value will also be provided for the comparison of daprodustat vs. rhEPO.
 
• On-treatment BP exacerbations will be summarized as follows: The number and percent of subjects with 0, 1, 2, 3, 4, 5 and >5 on-treatment BP exacerbations will be provided by treatment group. Additionally, the number and percent of subjects with on-treatment BP exacerbations and number of on-treatment BP exacerbation events will be provided by treatment group, in total and by BP exacerbation type (see Section 14.6.4). The total treatment exposure in years and overall on-treatment BP exacerbation rate per 100 PY will be provided by treatment group. 
 
○ The BP exacerbation summary above will be repeated for the following groups and BP values: 
 
▪ (1) All subjects, all on-treatment BP values (including both pre-dialysis and post-dialysis BP values)
 
▪ (2) All subjects, on-treatment post-dialysis BP values only
 
▪ (3) All subjects, on-treatment pre-dialysis BP values only.
 
 
 
 
 

Model Results Interpretation

 
• One-sided p-values will be compared to 0.025 to assess nominal significance.
 

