## CONFIDENTIAL

204837

Parameter	Study Assessments Intended as Baseline		Baseline Used in Data Display
	Screening (Week -4)	Day 1 (Pre-Dose)	
hematology, other laboratory and hepatobiliary (liver) tests			
ECG 	X		Week -4
PRO			
PGI-S		X	Day 1

NOTE: Unless otherwise stated, the mean of replicate assessments at any given time point will be used as the value for that time point.

[1]: Baseline monthly IV iron dose will be defined as total IV iron (mg) over the 12 weeks prior to randomization. See Section 14.6.3.

[2]: Post-dialysis baseline values for SBP, DBP, MAP, HR, and weight will be defined as the latest non-missing pre-dose assessment before the randomization date. This will most often be the value recorded at the Week -4 visit. However, for cases where the treatment start date falls after the randomization date, the randomization date will be used as the baseline measurement.

[3]: The Week -4 (screening) ECG must be performed pre-dialysis, and may be performed on any dialysis day from the Week -4 visit to the Day 1 visit, except during the first dialysis session of the week. Two additional ECGs are required if the screening ECG indicates prolonged QTc. In this case, the average QTcB value of all three ECGs will be used as the baseline QTcB.

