**Blood Pressure Exacerbations**

- BP exacerbations will be defined as (SBP  $\geq$  25 mmHg increase from baseline or SBP  $\geq$  180 mmHg or DBP  $\geq$  15 mmHg increase from baseline or DBP  $\geq$  110 mmHg) and grouped by type as follows:
  - BP exacerbations
    - SBP exacerbations
      - SBP  $\geq$  25 mmHg increase from baseline or
      - SBP  $\geq$  180 mmHg
        - SBP  $\geq$  180 mmHg and baseline SBP < 180 mmHg (including subjects with a missing baseline SBP)
        - SBP  $\geq$  180 mmHg and baseline SBP  $\geq$  180 mmHg
    - DBP exacerbations
      - DBP  $\geq$  15 mmHg increase from baseline or
      - DBP  $\geq$  110 mmHg
        - DBP  $\geq$  110 mmHg and baseline DBP < 110 mmHg (including subjects with a missing baseline DBP)
        - DBP  $\geq$  110 mmHg and baseline DBP  $\geq$  110 mmHg

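### The BP exacerbation rate model leaves out baseline BP, although the event is defined partly relative to baseline, so its confidence interval is likely somewhat wider than needed

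*SAP*

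**What the plan says.** SAP Section 8.1 (Blood Pressure, Model Specification) sets out three BP models.

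- **Exacerbation rate.** Within-group rates, the rate ratio, its two-sided 95% CI and a one-sided p-value come from a "negative binomial model with treatment and the prognostic randomization strata as covariates and the logarithm of time on-treatment as an offset variable". The stratification factor is region.
- **Change to Week 52 (MMRM).** The terms include "baseline BP parameter and the baseline BP parameter by time and treatment by time interaction terms".
- **Change to end of treatment (ANCOVA).** The terms are treatment, region "and the corresponding baseline BP parameter".

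Section 14.6.4.2 defines an exacerbation by any one of four criteria. The SBP part joins a relative and an absolute test: at least a "25 mmHg increase from baseline or SBP" of at least 180 mmHg. The DBP part does the same with a rise of at least 15 mmHg or a level of at least 110 mmHg. Scheduled and unscheduled on-treatment readings count, with at most one event per date in the total.

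The analysis uses post-dialysis BP, and List of Data Displays Table 3.014 confirms this for the model. The post-dialysis baseline is the last pre-dose value before the randomization date. Section 5.2.1, note 2, adds: "This will most often be the value recorded at the Week -4 visit". Protocol Section 9.4.2 takes triplicate readings only on Day 1, at Week 52 and at early treatment discontinuation, so the Week -4 value is normally one reading.

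**The concern.** One baseline reading is the comparator for every later visit. If it is low by chance, ordinary later readings clear the 25 or 15 mmHg rise again and again, and the participant's count is high all year. If baseline is high, the 180 and 110 mmHg thresholds are easier to reach. Baseline BP should therefore predict the count, perhaps in a U-shape.

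In a model with only treatment and region, that predictable variation is absorbed into the negative binomial dispersion and widens the CI for the rate ratio. The trial already collects the values, and Section 5.4.2 lists baseline post-dialysis SBP and DBP as continuous covariates for the change-from-baseline analyses.

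The endpoint is secondary, with a nominal one-sided 0.025 test. The protocol's benefit assessment (3.3.2) names avoiding rhEPO-related hypertension as a potential benefit, so precision here has some value.

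**Working it through.** **Inputs from the documents.** 402 randomized, 268 to daprodustat and 134 to epoetin alfa (Protocol 10.1.1); five regions (SAP 5.3); the four criteria; one baseline reading; and the model terms above. The documents state no exacerbation rate, dispersion, BP standard deviation or CI width, so there is no plan figure to reproduce for this endpoint. The trial's own sizing does reproduce: 1.96 × 1.5 × √(1/240 + 1/120) = 0.329 g/dL, against 0.33 stated. It has no bearing on BP.

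**Assumed.** SBP between-participant SD 15 to 25 mmHg, visit-to-visit SD 12 to 18, mean 138 or 150; DBP SDs 0.6 times these; participant drift over the year (a true change unrelated to baseline) with SD 0 to 15; 16 post-dialysis readings; about 20% stopping early; no drug effect.

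**Mechanism by hand.** With mean count μ and dispersion k, SE(log rate ratio) ≈ √[(1/268 + 1/134) × (1/μ + k)], where 1/268 + 1/134 = 0.01119.

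- SDs 15 and 15, no drift: μ = 3.22. Dispersion k is 1.09 without baseline and 0.68 with linear baseline terms. SE ≈ √(0.01119 × 1.401) = 0.125, falling to √(0.01119 × 0.991) = 0.105. The simulated values were 0.129 and 0.113.
- SDs 20 and 12, drift 15: μ = 3.40, k is 2.41 and 2.37. SE ≈ 0.174, falling to 0.173. The simulated value was 0.179 both times.

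The gain depends on how much of k the baseline explains.

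**Simulated mean reported SE (110 trials per row).**

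| Between SD / visit SD / drift | As planned | Linear baseline | With squares | Fall, linear / squares |
|---|---|---|---|---|
| 15 / 12 / 0 | 0.161 | 0.150 | 0.147 | 7% / 9% |
| 15 / 15 / 0 | 0.130 | 0.114 | 0.112 | 12% / 13% |
| 20 / 12 / 0 | 0.156 | 0.155 | 0.147 | 1% / 6% |
| 20 / 15 / 0 | 0.126 | 0.122 | 0.116 | 3% / 7% |
| 20 / 15 / 10 | 0.136 | 0.134 | 0.130 | 2% / 4% |
| 20 / 15 / 15 | 0.146 | 0.144 | 0.142 | 1% / 2% |
| 20 / 12 / 15 | 0.177 | 0.177 | 0.174 | 0% / 1% |
| 25 / 12 / 15, mean 150 | 0.161 | 0.158 | 0.154 | 2% / 4% |

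A further 250 trials in each of four assumed settings gave falls of about 1 to 17% (linear) and 4 to 17% (with squares).

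**Actual spread of the estimate.** This needs more trials. With 900 per setting (between SD 15 to 20, visit SD 13 to 18, 22% stopping early, no drift):

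| Setting | Reported SE: planned / linear / squares | Actual SD: planned / linear / squares |
|---|---|---|
| 1 | 0.119 / 0.101 / 0.101 | 0.108 / 0.102 / 0.099 |
| 2 | 0.130 / 0.119 / 0.117 | 0.118 / 0.116 / 0.116 |
| 3 | 0.150 / 0.146 / 0.142 | 0.134 / 0.134 / 0.133 |

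The actual SD falls by 0 to 6% (linear) or 1 to 8% (squares). The 250-trial runs gave about 0 to 10%, and none once drift was added. With drift SD 15, two 150-trial runs gave 0.131 to 0.133 and 0.153 to 0.155, again no gain. One 150-trial run (15 / 15 / 0) showed a larger fall, 0.115 to 0.098. Repeating it with 600 trials gave 0.121 to 0.114, a fall of 6%, so the larger figure looks like Monte Carlo error.

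As planned, the reported SE exceeds the actual spread by 10 to 12% (0.119/0.108, 0.130/0.118, 0.150/0.134). Part of the narrowing therefore removes a conservative SE rather than adding information.

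**On the CI scale.** In setting 2, at a rate ratio of 1, the 95% CI is exp(±1.96 × 0.130) = 0.775 to 1.290 as planned, and exp(±1.96 × 0.119) = 0.792 to 1.263 with linear terms.

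**The case against.** The planned model has a good defence.

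- **It is valid.** A reader might infer that the comparison is biased or that chance imbalance in baseline BP invalidates it. Neither follows: under randomization such imbalance is noise that the planned CI already allows for. This stands.
- **The definition is only partly relative.** A reader might take an exacerbation to be wholly baseline-relative. SBP of at least 180 and DBP of at least 110 mmHg count whatever the baseline. This stands, and it is why a linear term alone can gain little.
- **The choice fits a pattern.** The other two BP models analyse continuous change, each with one matching baseline. The SAP's event analyses, namely Cox models for rescue and transfusion and the CMH test for Hgb responders, also use only treatment and region. The omission therefore need not be an oversight. That does not make baseline less predictive here.
- **Adjustment has side effects.** The same model supplies within-group rates. With a log link, a rate predicted at mean baseline is not the population rate. In simulation (150 trials in each of three settings) the control rate fell 3 to 13% with linear terms. With squares it fell 9 to 13% if the squared columns were averaged, and 22 to 32% if evaluated at mean baseline. Section 14.6.4.2 also counts participants with a missing baseline through the absolute thresholds, and Section 5.2.2 leaves missing baselines missing, so a covariate would drop them. Both points stand and shape the fix.
- **Stakes are low.** The test is nominal and unadjusted for multiplicity, and Protocol 10.3.1 calls the secondary analyses exploratory. This stands.

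**Conclusion.** The point holds as a modest efficiency suggestion. The model omits a covariate that is built into two of the four event criteria and usually rests on one reading, so the CI is likely somewhat wider than needed. Across the assumed variances the reported SE falls by about 0 to 17% and the actual spread by about 0 to 10%. The gain is largest when visit-to-visit noise is large relative to differences between participants, and it may vanish if participant-level drift dominates. None of these inputs is in the documents, so no single figure can be claimed.

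Two stronger readings are not supported: that the analysis is biased or in error, and that a gain near the top of the range can be expected. No trial decision rests on this interval.

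**What to change.** Before unblinding, amend SAP Section 8.1 as follows.

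1. Add baseline post-dialysis SBP and DBP, with squared terms because both low and high baselines can raise the count, to the negative binomial model for the rate ratio, its CI and p-value.
2. State that a missing baseline will be filled with a simple value, for example the overall mean, so that participants counted through the absolute thresholds stay in the model.
3. Report within-group rates either from the current model or by averaging predictions over all participants, not at the mean baseline.

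Only post-dialysis baselines are needed. Table 3.014 fits the model once, to post-dialysis BP, and the pre-dialysis repeat in Section 8.1 is of the descriptive summary.

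The cost is slightly more SAP wording and programming. No new data are required.

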## 8.2. Exploratory Safety Analyses

### *Exploratory Cardiovascular Safety Analysis*

Exploratory CV Safety Analyses
Endpoint(s):

 
• MACE (composite of all-cause mortality, non-fatal MI, or non-fatal stroke)
 
• MACE or a thromboembolic event (vascular access thrombosis, a symptomatic deep vein thrombosis or a symptomatic pulmonary embolism)
 
• MACE or hospitalization for HF
 
• All-cause mortality
 
• CV mortality
 
• MI (fatal and non-fatal)
 
• Stroke (fatal and non-fatal)
 
• CV mortality or non-fatal MI
 
• All-cause hospitalization
 

Model Specification

 
• For all exploratory CV endpoints, confidence intervals for the rate per 100 person-years will be reported. For within-group rates, the 95% CI will be obtained using an exact Poisson method. For difference in rates between treatments, the two-sided 95% CI will be constructed with a normal approximation using Walds' method [Liu 2006].
 
• For the MACE endpoint, the calculation of time-to-event or censoring is described in further detail in Section 14.6.4.
 
• First occurrence of adjudicated MACE for a subject is defined as the first adjudicated event, determined by the event date, which is indicated as all-cause mortality, non-fatal MI or non-fatal stroke with further details in Section 14.6.4.
 
• For those endpoints or components of endpoints intended to go through the adjudication process, only the adjudicated results will be used.
 

Model Results Presentation

 
• A summary of the number and percentage of subjects having first-occurrence MACE will be provided by treatment group. The number and percentage of the types of events that make up the first occurrence of MACE will also be provided by treatment group. This summary table will be repeated for MACE plus thromboembolic events, for MACE plus hospitalization for heart failure and for MACE plus thromboembolic events or hospitalization for CHF.
 
• A summary of all MACE including the number and percentage of subjects and number of events (including first and subsequent MACE) by type of event will be provided by treatment group.
 
• A summary of the number and percentage of subjects having first-occurrence adjudicated COVID-19 MACE will be provided by treatment group. The number and percentage of the types of events that make up the first occurrence of adjudicated COVID-19 MACE will also be provided by treatment group.
 
• Summaries of adjudication details of all-cause mortality will include the number and percentage of subjects by cause of death.
 
• Summaries of adjudication details of MI will include the number and percentage of events by outcome of MI (fatal or non-fatal), type of MI, increased cardiac markers (y/n), ST segment classification [ST-elevation myocardial infarction (STEMI), non-ST-elevation myocardial
 

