10.1. Sample Size Determination

10.1.1. Sample Size Assumptions

The size of this study has been determined to be sufficient to meet the ICH E1 guideline for participant exposure, number and duration and to provide at least 90% power to test the primary non-inferiority hypothesis with a two-sided 95% CI.

Approximately 402 participants are planned to be randomized in a 2:1 ratio to daprodustat or rhEPO (268 to the daprodustat arm and 134 to the rhEPO arm), in order to provide at least 100 participants exposed to daprodustat for one year. Participants will be treated to achieve and maintain Hgb between 10 and 11 g/dL. The expected difference in mean Hgb change from baseline and the EP, between arms, is 0 g/dL and the anticipated between participant standard deviation (SD) is 1.5 g/dL, based on historical rhEPO trials and daprodustat clinical trial experience to date. With a prespecified non-inferiority margin of -0.75 g/dL, a two-sample T-test and assuming that up to approximately 10% of

participants will have no Hgb values measured during the EP, 402 randomized participants will provide >90% power to test the primary hypothesis.

With 402 randomized participants, it is anticipated that the difference in mean Hgb change from baseline between arms will be estimated with a precision of 0.33 g/dL (half width of the two-sided 95% CI) and the largest (most negative) difference between arms that would meet the statistical criterion for non-inferiority would be -0.42 g/dL.

Note: Country-specific requirements for France for the sample size consideration are provided in [Appendix 8](#) (see Section 12.8.1, Item 2 for details).

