10.3.2. Safety Analyses

All safety analyses will be performed on the Safety Population.

Endpoint	Statistical Analysis Methods
Adverse Events	All AEs (i.e. Non-serious, serious, and AEs of special interest) will be descriptively summarized by treatment group.
Vital signs	Summary statistics at each visit will be generated by treatment group
Laboratory data	Summary statistics at each visit will be generated by treatment group. Number of participants who meet protocol defined stopping criteria (e.g. liver chemistry) will be summarized by treatment group.
Randomized	The number of participants who discontinued randomized treatment will be

Endpoint	Statistical Analysis Methods
treatment discontinuations	summarized by reason for discontinuation and treatment group. The time to discontinuing randomized treatment will be presented graphically and assessed.
Cardiovascular Safety Endpoints	This study is not designed or sufficiently powered for formal statistical analyses to assess cardiovascular safety. With fewer than 80 first-occurrence MACE (defined as all-cause mortality, non-fatal MI, or non-fatal stroke) expected to occur during the trial, incidence rates and two-sided 95% CIs will be computed for the following mortality and CV composite or component endpoints: 1) MACE; 2) MACE or a thromboembolic event (vascular access thrombosis, a symptomatic deep vein thrombosis or a symptomatic pulmonary embolism); 3) MACE or hospitalization for heart failure; 4) all cause mortality; 5) CV mortality; 6) MI (fatal and non-fatal); 7) stroke (fatal and non-fatal); 8) CV mortality or non-fatal MI; 9) all cause hospitalization.

Full details of all safety data reporting will be described in the RAP.

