**CONFIDENTIAL**

204837

- If the category cannot be refined further, then descriptive rather than statistical comparisons may be performed for the particular subgroup. If there are less than 25 subjects in one of the subgroup categories with two levels (e.g., history of stroke (Yes/No)), then statistical comparison will not be performed for that subgroup. Due to small sample sizes in American Indian or Alaskan Native, Native Hawaiian or Other Pacific Islander, and Mixed Race categories, statistical comparison for race group will include Asian, Black or African American, and White categories only. For baseline Hgb subgroup, if there are fewer than 25 subjects in the category  $<9$  g/dL, the categories  $<9$  g/dL and  $9 - <10$  g/dL will be combined to  $< 10$  g/dL.
- A pre-specified strategy for prioritizing subgroups/covariates is defined below (as recommended in the 2015 draft Committee for Medicinal Products for Human Use (CHMP) guidance on the investigation of subgroups in confirmatory clinical trials)
- The primary and principal secondary endpoints will be evaluated for the subgroups below. Although subgroup analyses are aimed to assess for consistency with the overall results, they may have low power, especially if the subgroup is small or has a low number of events. Statistical models (ANCOVA) will be adjusted for the covariates used in the original analysis, subgroup, treatment and treatment by subgroup interaction. For the subgroup Regions combined (USA vs. non-USA), the randomization stratification factor Region (with 5 levels, Regions 1- 5) will not be included in the statistical model.
- For subgroup analyses of time-to-event endpoints, point estimates and confidence intervals for the rate per 100 person-years will be reported for each treatment group within a subgroup, as well as the point estimate and two-sided 95% CI for the difference in rates between treatments within a subgroup. For within-group rates, the two-sided 95% CI will be obtained using an exact Poisson method. For difference in rates between treatments, the two-sided 95% CI will be constructed with a Normal approximation using Wald's method [Liu, 2006].

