**CV Safety Endpoints**

- First event person years = (cumulative total time to first event for subjects who have the event + cumulative total of censoring time for subjects without the event) / 365.25
- First event incidence rate (per 100 person years) = (100 \* number of subjects with at least 1 event) / first event person years
- First event absolute rate difference (per 100 person years) = daprodustat incidence rate (per 100 person years) – rhEPO incidence rate (per 100 person years)

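### The Wald interval for rate differences can falsely exclude zero in up to about 9% of trials rather than 5% when roughly 3 to 15 events are expected, nearly always as a spurious excess on daprodustat

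*SAP*

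**What the plan says.** SAP Section 8.2 (Exploratory Cardiovascular Safety Analysis) lists nine endpoints, from MACE down to MI, stroke and CV mortality. Within each arm: "For within-group rates, the 95% CI will be obtained using an exact Poisson method". Between arms: "For difference in rates between treatments, the two-sided 95% CI will be constructed with a normal approximation", by Wald's method. Section 14.6.4.1 defines the rate as subjects with a first event divided by first-event person-years. The same between-arm sentence appears in Section 5.4.2 (subgroup analyses of time-to-event endpoints), Section 7.3.1 (Time to Rescue) and Section 14.6.3.4 (time to first transfusion).

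None of these sections prints the variance formula or gives a rule for a zero-event arm or low counts. The SAP does restrict sparse displays elsewhere: Section 5.4.2 drops comparisons for two-level subgroups when a category has fewer than 25 subjects, and Section 8.3.1 drops some adverse-event plots below 20 subjects. Neither rule covers the CV endpoint intervals.

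Protocol Section 10.1.1 plans "268 to the daprodustat arm and 134 to the rhEPO arm". Protocol Section 10.3.2 says the trial is not powered for cardiovascular safety and gives one expected count: "With fewer than 80 first-occurrence MACE (defined as all-cause mortality, non-fatal MI, or non-fatal stroke) expected to occur during the trial". It gives none for any component.

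**The concern.** The plan uses an exact method where one arm is described and a large-sample approximation where two arms are compared, which is where low counts do more damage. If one arm has no events, an unpooled Wald interval treats that arm's rate as known to be exactly zero. The epoetin alfa arm has half the person-time, so it is the more likely to be empty, and the error then points one way: towards more events on daprodustat.

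Section 8.2 plans no p-value or hazard ratio for the adjudicated CV endpoints, so this interval is the only between-arm inference a reader will have for stroke or MI. One that excludes zero is likely to be read as a signal, even when the split is unremarkable under equal rates and the exact within-arm limits beside it overlap.

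**Working it through.** **Inputs.** Allocation is 268 to 134 (Protocol 10.1.1). Person-years are not stated; 268 and 134 are assumed, one year per participant. Error rates depend on the expected total and the 2:1 ratio, hardly at all on this scale: 255 and 127 person-years give the same picture. The variance formula is assumed to be the standard unpooled one.

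**Formula.** With x and y events in T1 and T2 person-years, the Wald interval is (x/T1 − y/T2) ± 1.96·√(x/T1² + y/T2²).

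**Zero-event case.** If y = 0, the lower limit is (x − 1.96√x)/T1. It is positive once √x > 1.96, that is from x = 4.

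- 3 versus 0: −0.15 to 2.39 per 100 person-years, includes zero.
- 4 versus 0: difference 4/268 = 1.49, standard error √4/268 = 0.75, interval 0.03 to 2.96, excludes zero.
- Given four events and equal rates, P(4 versus 0) = (2/3)⁴ = 16/81 = 19.8%. The reverse split, 0 versus 4, has probability (1/3)⁴ = 1/81 and also excludes zero. Together, 17/81 = 21.0% of trials with exactly four events exclude zero falsely. With exactly five or six events the figures are 13.6% and 10.6%; with exactly three, 0%.

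**Alternatives for 4 versus 0.** The exact Poisson limits are 0.41 to 3.82 for 4/268 and 0 to 2.75 for 0/134.

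- MOVER lower limit: 1.49 − √[(1.49 − 0.41)² + (2.75 − 0)²] = 1.49 − 2.96 = −1.47. Upper limit: 1.49 + (3.82 − 1.49) = 3.82.
- Score interval: −1.37 to 3.84. It first excludes zero at 8 versus 0.

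**Error rates.** All pairs of independent Poisson counts were enumerated under equal rates at 2:1, against the nominal 5% (2.5% per side):

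| Expected events, total | Wald, two-sided | Wald, daprodustat higher | Wald, daprodustat lower |
|---|---|---|---|
| 1 | 0.4% | 0.4% | 0.02% |
| 2 | 2.5% | 2.4% | 0.2% |
| 3 | 5.6% | 5.3% | 0.4% |
| 4 | 8.0% | 7.4% | 0.6% |
| 5 | 9.0% | 8.1% | 0.8% |
| 6 | 8.9% | 7.9% | 1.0% |
| 8 | 7.6% | 6.3% | 1.2% |
| 10 | 6.5% | 5.2% | 1.3% |
| 15 | 6.0% | 4.7% | 1.3% |
| 20 | 5.7% | 4.4% | 1.3% |
| 40 | 5.3% | 3.7% | 1.6% |
| 80 | 5.1% | 3.2% | 1.9% |

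The two-sided peak is 9.0%, at 5.5 expected events, and the rate exceeds 6% only from about 3.25 to 14.75. A subject-level simulation (268 and 134 participants, one-year follow-up, 40,000 runs) agrees: 5.5%, 8.9%, 6.4% and 4.8% at 3, 6, 10 and 80 expected events.

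**Cause.** At five expected events, 8.1 of the 9.0 points come from outcomes with no epoetin alfa events. At 1:1 allocation the rate would be 4.6%, so the unequal allocation drives the excess.

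**Replacements.** MOVER keeps each side at or below about 2.1%. The score interval has two-sided error of 4.0% to 4.9% at 3 to 80 expected events, but its daprodustat-lower side reaches about 3.9% at around four expected events.

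**The case against.** Several stronger readings are tempting, and the documents do not support them.

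- *That the stated 95% is badly wrong whenever events are few.* The worst two-sided error is 1.8 times nominal (9.0/5), in a limited band. Below about 3 expected events the interval is conservative, so the very rarest endpoints are not the problem.
- *That MACE is affected.* The protocol figure is an upper bound, but at 40 to 80 events two-sided error is 5.1% to 5.3%. Only a mild imbalance between sides remains.
- *That stroke, MI or CV death are known to fall in the band.* No component counts are given.
- *That no other between-arm view exists.* Section 8.2 plans a Kaplan-Meier plot for MACE, and Section 8.3.1 plans relative risks for investigator-reported events of special interest. Rescue and transfusion have Cox models, so the rate difference is supplementary there.
- *That events over squared person-time is the SAP's own formula.* The SAP cites a paper for the method and does not print it.

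It is also fair to say that no threshold or decision hangs on these intervals, that counts and exact within-arm limits appear beside them, and that the error runs against the sponsor's own product.

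All of this limits the size and importance of the point. It does not remove it: an exploratory interval labelled 95% should still be close to 95%, and a directional error in the only interval for the adjudicated endpoints is easy to avoid.

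**Conclusion.** The point holds in a limited form, as something to consider. Assuming the unpooled variance and 2:1 person-time, the planned interval excludes zero falsely in at most about 9% of trials against 5%, when about 3 to 15 events are expected in total. On the side showing an excess on daprodustat, the error is up to about 8% against 2.5%. Outside that band the two-sided level is conservative or close to nominal. Whether any CV endpoint falls inside it cannot be settled from the documents. The primary and principal secondary analyses are untouched.

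**What to change.** In SAP Sections 5.4.2, 7.3.1 (Time to Rescue), 8.2 and 14.6.3.4, replace the Wald interval for the rate difference with the MOVER interval built from each arm's exact Poisson limits, and write out the formula. A score interval is an acceptable alternative. It sits closer to 5% overall but shifts some error to the daprodustat-lower side at low counts, whereas MOVER controls both sides and is mildly conservative. Specify the choice before unblinding, so that the method is not changed after an awkward 4-versus-0 result.

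The cost is SAP wording in four places and a few lines of code, with no effect on design or data collection. Intervals for rare endpoints widen, most visibly with an empty arm: at 4 versus 0 the width goes from 2.96 − 0.03 = 2.93 to 3.82 + 1.47 = 5.29 per 100 person-years. That extra width is uncertainty the Wald form leaves out.
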